6.2. Data management

Data is stored on secure Mass General Brigham corporate provisioned and backed up servers physically located in our Mass General Brigham corporate data centers. Mass General Brigham corporate data centers are designed to insure availability of the affiliated hospitals' and research applications and IT systems in the event of a disaster. The Division follows Mass General Brigham workstation requirements which include: encryption at rest, up-to-date malware protection including antivirus, spyware detection and removal tools, Crowdstrike End Point protection installed, devices enrolled in enterprise Mobile Device Management (MDM) solution as appropriate, any laptop/computer used for business purposes must not be shared with family, friends, or other unauthorized individuals, and compliance with enterprise Password Requirements. Only authorized personnel have read-only access to raw data files.

Cleaned and analysis-ready datasets, i.e., +/- imputed one-row-per-patient tables with all required exposure, outcome and covariate variables, are stored in separate sub-directories dedicated for the specific emulated trial.

6.3. Quality control

Upon delivery, data quality procedures included checks on delivered tables and variables, per table checks, descriptives on most important measures such as demographic and stage distributions by sex at time of initial diagnosis, regimen/exposure frequency counts and time-trends and overall survival benchmarks against literature and general cancer registry statistics. The R code to reproduce the quality assessments is deposited on the Mass General Brigham-provisioned GitLab server https://gitlab.partners.org/drugepi/encore/quality (repository is only accessible within the Mass General Brigham network and additionally only to authorized study personnel).

² CDM = Common Data Model

6.4. Study design

Research design (e.g. cohort, case-control, etc.): Cohort study

[figure not shown]
Rationale for study design choice: Resembles the principles of the (target) trial emulation framework.9

6.5. Study design diagram

Figure 1 depicts study design and variable measurement considerations for the emulation of the FLAURA trial. The selection of key confounders/prognostic factors is driven by expert knowledge and additionally based on covariates included in the real-world prognostic score (ROPRO) which is a published and validated pan-tumor and cancer-specific prognostic score framework for overall survival.¹⁰⁻¹⁴

Figure 1. Study design illustration for FLAURA trial emulation.

Cohort Entry Date (Initiation of 1L osimertinib versus gefitinib or erlotinib) Day 0

- b. De novo metastatic status, time initial diagnosis to T0, time from first evidence of metastatic disease to T0, # metastatic sites, smoking, family history, race/ethnicity, etc.
- c. Labs (albumin, hemoglobin, etc.) and vitals (BMI, etc.) that are part of the ROPRO prognostic score; see Becker, Weberpals, et al. Ann Oncol 2020 (doi: 10.1016/j.annonc.2020.07.013)
- d. No observability criterion was applied since measures like continuous enrollment periods (claims data) are not available in electronic health records.
- 1L = First-line antineoplastic systemic therapy

6.6. Setting

6.6.1. Context and rationale for definition of time 0 (and other primary time anchors) for entry to the study population

Time 0 in this database study is defined as the date a patient initiated osimertinib (exposure) or erlotinib or gefitinib (comparator) as part of their 1L systemic antineoplastic treatment for advanced or metastatic NSCLC. This aims to emulate the date of randomization and cohort entry in the RCT (the time from randomization to first dose is not reported in the clinicaltrials.gov study report or the trial articles).

6.6.2. Context and rationale for study inclusion criteria

Study inclusion criteria were defined to emulate all key inclusion criteria for the trial that were deemed both clinically relevant and measurable in EHR data. See Excel appendix table 1 (Table1_I_E) for a one-by-one evaluation. A summary of the operational definitions of the inclusion criteria that were applied for each database can be found in the Excel appendix table 2. A flowchart of the study cohort assembly is provided in Appendix 3.

In the RCT, 95% of patients were metastatic at date of randomization while only the remaining 5% were locally advanced, not amenable to curative surgery or radiotherapy. Since locally advanced line settings are readily curated in EDB1 only, we will restrict the analysis in EDB2 and EDB4 to only patients with any evidence of metastases prior to or on index date (more details see below in 6.4.4).

6.6.3. Context and rationale for study exclusion criteria

Study exclusion criteria were defined to emulate all key exclusion criteria for the trial that were deemed both clinically relevant and measurable in EHR data. See Excel appendix table 1 (Table1_I_E) for a one-by-one evaluation. A summary of the operational definitions of the exclusion criteria that were applied for each database can be found in the Excel appendix table 2. A flowchart of the study cohort assembly is provided in Appendix 3.

6.6.4. Context and rationale for exposure(s) of interest

The exposure and comparator were defined to emulate the agents compared for the trial, i.e., initiation of osimertinib versus erlotinib or gefitinib in a 1L metastatic setting.

- EDB1: Exposure is derived using a manually curated line of therapy (LOT) table provided by the data partner that programmatically categorizes treatment regimens into a coherent line of treatment. That is, each patient is represented with one row per curated line of therapy with corresponding information on line number, regimens as well start and end dates. Based on this table, patients are identified who received osimertinib, erlotinib or gefitinib treatment regimen by their generic names (string match) in 1L. The LOT implicitly only considers regimens that were given as part of a metastatic disease setting.

 More details and annotated code to identify initiators can be found in the 'Derive cohort EDB1' Quarto report (access within MGB network only).
- EDB2: Exposure is derived using a manually curated line of therapy (LOT) table provided by the data partner that programmatically categorizes treatment regimens into a coherent line of treatment. That is, each patient is represented with one row per curated line of therapy with corresponding information on line number, regimens as well start and end dates. Based on this table, patients are identified who received osimertinib, erlotinib or gefitinib treatment

regimen by their generic names (string match) in 1L. The LOT implicitly only considers regimens that were given as part of a metastatic disease setting. More details and annotated code to identify initiators can be found in the 'Derive cohort EDB2' Quarto report' (access within MGB network only).

• EDB4: For the EDB4 database, the following logic is applied (see Figure 2). First, patients are identified who have ever initiated any of osimertinib, erlotinib or gefinitib. If patients initiated more than one of these three regimens simultaneously, these patients are not considered and will be excluded. To guarantee that the osimertinib, erlotinib or gefinitib are initiated in a 1L metastatic setting, patients are only considered if there is any evidence of a metastatic diagnosis before the index date. Additionally, if patients received any other antineoplastic drug before the initiation of any of the study drugs that is typically used for the 1L metastatic setting according to NCCN guidelines or expert knowledge, these patients will not be considered either (see list below*). This may decrease sensitivity as some of these drugs may be also used for the (neo)adjuvant setting but increase specificity in the selection of initiators in the 1L metastatic setting. More details and annotated code to identify initiators can be found in the 'Derive cohort EDB4' Quarto report (access within MGB network only).

*Antineoplastic drugs considered: afatinib, alectinib, amivantamab, atezolizumab, bevacizumab, brigatinib, cabozantinib, capmatinib, carboplatin, cemiplimab, ceritinib, cisplatin, cobimetinib, crizotinib, dabrafenib, dacomitinib, docetaxel, durvalumab, encorafenib, erlotinib, etoposide, fam-trastuzumab deruxtecan-nxki, gefitinib, gemcitabine, ipilimumab, larotrectinib, lorlatinib, mobocertinib, necitumumab, nivolumab, osimertinib, paclitaxel, pembrolizumab, pemetrexed, pralsetinib, ramucirumab, selpercatinib, tepotinib, trastuzumab, trastuzumab, trastuzumab-anns, trastuzumab-deruxtecan, trastuzumab-deruxtecan, trastuzumab-dkst, tremelimumab, vemurafenib, vinorelbine

Extract the date of first exposure => index date

Exclude patients who initiated more than one FLAURA drugs on the same date

Exclude patients who have received any other antineoplastic drug approved for advanced/metastatic NSCLC before their index date

Restriction to evidence of metastases before index date and general eligibility criteria

Figure 2. Identification of study drug initiators in EDB4

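### No written exposure rule requires the study drug to be used alone: EDB4 admits a partner drug started the same day, and EDB1 and EDB2 leave the match type open

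*Protocol*

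**What the plan says.** Section 6.6.4 of the protocol gives the aim: "The exposure and comparator were defined to emulate the agents compared for the trial". The Abstract and Section 4 describe each FLAURA arm as one oral drug. Table 2 states the same treatment strategies for the trial and the emulation.

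**EDB1 and EDB2.** Initiators come from a line-of-therapy table in which "each patient is represented with one row per curated line of therapy with corresponding information on line number, regimens as well start and end dates". From that table, "patients are identified who received osimertinib, erlotinib or gefitinib treatment regimen by their generic names (string match) in 1L". Section 6.6.1 sets time 0 at the date the study drug was initiated "as part of their 1L systemic antineoplastic treatment for advanced or metastatic NSCLC".

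**EDB4.** Section 6.6.4 writes the rules out. On simultaneous starts: "If patients initiated more than one of these three regimens simultaneously, these patients are not considered and will be excluded". On other drugs, Figure 2 has the step "Exclude patients who have received any other antineoplastic drug approved for advanced/metastatic NSCLC before their index date". The accompanying drug list includes carboplatin, pemetrexed and bevacizumab, and also the three study drugs.

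Further detail lies outside the document. For EDB1, "More details and annotated code to identify initiators can be found in the 'Derive cohort EDB1' Quarto report". Section 6.6.3 adds that a summary of the "operational definitions of the exclusion criteria that were applied for each database can be found in the Excel appendix table 2". Neither source is at hand.

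**The concern.** Time 0 should mark the start of the strategy being compared. If some patients start the study drug together with chemotherapy or an antiangiogenic agent, their strategy is not the one FLAURA tested, although they are counted as initiators. If such use differs between arms, part of the estimated contrast belongs to the partner drug.

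Nothing later in the plan would pick this up. Table 5 has no covariate for concurrent treatment, so the propensity score cannot balance it. None of the 12 sensitivity analyses in Table 9 restricts to single-agent use. The intention-to-treat rationale in Section 6.6.6 concerns treatment after the assigned drug, not what is started with it.

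Section 7 says that calendar year perfectly predicts treatment. Any difference in combination use between eras would therefore appear as a difference between arms. The protocol gives no evidence that such a difference exists.

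**Working it through.** **1. Search for a single-agent condition.** Sections 5 and 6.6.1 to 6.6.4, Table 2, Table 5 and Table 9 contain none. The terms monotherapy and single agent do not occur in the text at hand.

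**2. Apply the EDB4 rules to four hypothetical patients.** All have evidence of metastasis and are otherwise eligible.

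| Pattern | Two study drugs on one date? | Other listed drug before index? | Result |
|---|---|---|---|
| Erlotinib alone | no | no | enters |
| Erlotinib and osimertinib, same day | yes | no | removed |
| Bevacizumab one day before erlotinib | no | yes | removed |
| Bevacizumab and erlotinib, same day | no | no | **enters as an erlotinib initiator** |

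The last row follows from the rules as written. One day separates it from a patient who is removed.

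**3. Apply the EDB1 and EDB2 rule to a first-line row listing erlotinib and bevacizumab.** An exact match on the whole regimen does not select the row. A match on the name anywhere in the regimen does. The protocol says only that it is a string match, so two analysts could build different cohorts from the same sentence.

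**4. Size.** No count of combination starters is given, so the following is illustration only. Assume a true HR of 0.80, a share f of one arm on a combination, and a partner-drug mortality HR of h against the TKI alone, averaged on the log scale:

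- combinations in the comparator arm only: HR = 0.80 / h^f
- combinations in the osimertinib arm only: HR = 0.80 × h^f
- the same f and h in both arms: the terms cancel and the HR stays at 0.80

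| f | h | Comparator arm only | Osimertinib arm only |
|---|---|---|---|
| 5% | 0.9 | 0.804 | 0.796 |
| 5% | 0.7 | 0.814 | 0.786 |
| 10% | 0.9 | 0.808 | 0.792 |
| 10% | 0.7 | 0.829 | 0.772 |

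For example, 0.7^0.10 = 0.965, and 0.80 / 0.965 = 0.829. The values of f and h are assumptions without support in the protocol.

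**5. Possible loss of power from the fix.** Section 10.3 states 80% power at HR 0.80 with two-sided alpha 0.05. The event count is not in the text, so the figure can only be inverted. Schoenfeld with 1:1 groups gives 4 × (1.960 + 0.842)² / (ln 0.80)² = 631 events. If the filter removed 2%, 5% or 10% of these, 618, 599 or 568 would remain, with power of 79.2%, 78.0% or 75.8%. These shares are also assumptions.

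**The case against.** The strongest reply is that the rule for the primary database may already be right. A string match on a regimen called osimertinib is naturally read as a match on the whole regimen name, and that would select single-agent regimens only. The code, the Excel appendix and the attrition diagrams are not at hand, and any of them may contain the restriction. This stands. A reader might infer that EDB1 and EDB2 take in every first-line regimen that names a study drug, but that presumes a partial match which the protocol does not state.

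A reader might also take the phrase in Section 6.6.1 about being part of first-line treatment as permission for combinations. It only places the drug in the first-line setting. Nor do the documents support the inference that time 0 could be an earlier line start, adding guaranteed survival time. Section 6.6.1 defines time 0 as initiation of the study drug, and Figure 2 uses the date of first exposure in EDB4.

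It is also fair to say that EDB4 enters only sensitivity analysis #11. Section 7 holds that, apart from the introduction of osimertinib, treatment for this population did not change materially, which weighs against a large difference in combination use by era.

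What the reply does not remove is the EDB4 rule. It is stated in full, and it admits same-day combination starters when followed as written. In EDB1 and EDB2 the selection sentence remains ambiguous on a core element of the emulation.

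**Conclusion.** The point holds in a limited form. No exposure rule in the protocol text requires single-agent use. In EDB4 this is a gap in an explicit rule, and it affects sensitivity analysis #11 only. In EDB1 and EDB2 it is an unstated match type, so combination starters are not ruled out; the text does not show that they are included.

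The size and direction of any bias are unknown. Under the assumed shares and partner effects, the HR moves from 0.80 to between 0.772 and 0.829, with the sign set by which arm holds the combinations. These shifts are small beside the trial interval of 0.64 to 1.00. A reader might infer that the primary estimate is biased in a known direction; the documents give no count that would support this.

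**What to change.** In Section 6.6.4:

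- **EDB1 and EDB2:** state that the study drug must be the whole first-line regimen, identified by an exact match on the full regimen entry.
- **EDB4:** extend the exclusion for other listed antineoplastics to those started before or on the index date, in both the text and Figure 2. Limit this to non-study drugs. The list includes the three study drugs, so a literal extension would remove every patient through the index drug itself.
- **All three databases:** show the step in the attrition diagrams, with the number of combination starters removed per arm.

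The cost is one filter per database, a few lines of text and probably a small loss of patients. If the EDB1 code already matches exactly, only the wording changes there and the primary cohort stays the same. One check is needed: the protocol does not say how the regimen entry is assembled. If it can include drugs started after time 0, a whole-regimen match would use later information, and the text should say how that is handled.

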Outcome:	Time to all-cause mortality (OS)		
Time (when follow up begins and ends):	From the day of treatment initiation until death or last observed clinical activity/last sign of the patient being alive or data cut-off, whichever occurred earlier		
Setting:	1L EGFRm+ metastatic NSCLC		
Main measure of effect:	Primary: Hazard ratio (95% CI) for overall survival		
	Secondary: median overall survival time (difference) in % (95% CI)		

The emulation of the main protocol elements of the FLAURA is illustrated side by side in **Table 2**.

Table 2. Trial emulation table summarizing the main protocol elements of the FLAURA trial and the planned emulation.

Protocol component	FLAURA RCT	Emulation	
Eligibility criteria	 - Age at least 18 years at time of randomization - Adenocarcinoma of the lung - Locally advanced or metastatic NSCLC, not amenable to curative surgery or radiotherapy - Tumour harbours one of the 2 common EGFR mutations known to be associated with EGFR-TKI sensitivity (Ex19del, L858R), either alone or in combination with other EGFR mutations - Patients must be treatment-naïve for locally advanced or metastatic NSCLC and eligible to receive first-line treatment with gefitinib or erlotinib 	there needs to be evidence of metastatic disease at time of treatment initiati (EDB4) - Evidence of any EGFR mutation in the 180 days before/on treatment initiati - Treatment needs to be first-line for advanced (EDB1) or metastatic (EDB2) disease or patients with prior exposure to any potential antineoplastic treatment	
Treatment	 World Health Organization Performance Status of 0 to 1 No prior treatment with any systemic anti-cancer therapy for locally advanced/metastatic NSCLC No prior treatment with an EGFR-TKI. osimertinib versus SoC EGFR-TKI (erlotinib or gefitinib) 	osimertinib versus SoC EGFR-TKI (erlotinib or gefitinib)	
strategies Assignment procedures	Random assignment to receive either osimertinib or SoC EGFR-TKI (gefitinib or erlotinib) in a 1:1 ratio	1:1 matching of patients based on their propensity to initiate osimertinib as opposed to SoC EGFR-TKI	
Follow-up period	Time from randomization until death from any cause or censoring of patients who did not die on the basis of the last recorded date that the patient was known to be alive	Time from treatment initiation until death from any cause or censoring of patients who did not die on the basis of the last recorded date that the patient was known to be alive	
Outcome	Overall survival	Overall survival	

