Time between earliest evidence of a metastatic and index date	c_time_met_dx_to_index	edbx_get_diagnosis_solid()	Time in days between earliest evidence of a metastatic and index date	Continuous	[-inf;0]
Histology (adenocarcinoma)	c_histology_match	edbx_get_histology()	Evidence of adenocarcinoma histology (non-squamous cell for EDB1)	Binary logical (TRUE, FALSE)	[-inf;0]
Albumin	c_albumin_g_l_cont	edbx_get_labs()	Closest albumin measurement (in serum/plasma) relative to index date in g/L. In case of ties, the lower is selected	continuous	[-90;0]
Alkaline phosphatase (ALP) ²	c_alp_u_l_cont	edbx_get_labs()	Closest alkaline phosphatase measurement (in serum/plasma) relative to index date in U/L. In case of ties, the lower is selected	continuous	[-90;0]
Alanine aminotransferase (ALT) ²	c_alt_u_l_cont	edbx_get_labs()	Closest alanine transaminase measurement (in serum/plasma) relative to index date in U/L. In case of ties, the lower is selected	continuous	[-90;0]

Characteristic	Harmonized analysis variable name	R function to derive covariate (see pdf in appendix)	Details ¹	Variable encoding	Assessment window
Aspartate aminotransferase (AST)	c_ast_u_l_cont	edbx_get_labs()	Closest aspartate aminotransferase measurement (in serum/plasma) relative to index date in U/L. In case of ties, the lower is selected. Used to compute AST-ALT ratio	continuous	[-90;0]
AST/ALT ratio	c_ast_alt_ratio_cont	edbx_get_labs()	AST/ALT ratio calculated from c_ast_u_l_cont/c_alt_u_l_cont	continuous	[-90;0]
Bilirubin ²	c_bilirubin_mg_dl_cont	edbx_get_labs()	Closest bilirubin measurement (in serum/plasma) relative to index date in mg/dL. In case of ties, the lower is selected	continuous	[-90;0]
Calcium ²	c_calcium_mg_dl_cont	edbx_get_labs()	Closest calcium measurement (in serum/plasma) relative to index date in mg/dL. In case of ties, the lower is selected	continuous	[-90;0]
Chloride	c_chloride_mmol_l_cont	edbx_get_labs()	Closest chloride measurement (in serum/plasma) relative to index date in mmol/L. In case of ties, the lower is selected	continuous	[-90;0]
Eosinophils/100 leukocytes ²	c_eosinophils_leukocytes_r atio_cont	edbx_get_labs()	Eosinophils/100 leukocytes in blood. In case of ties, the lower	continuous	[-90;0]
Glucose ²	c_glucose_mg_dl_cont	edbx_get_labs()	Closest glucose measurement (in serum/plasma) relative to index date in mmol/L. In case of ties, the lower is selected	continuous	[-90;0]

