Table 7. Primary and subgroup analysis specification

able 7. Primary and Subgroup	7 dilarysis specification
Hypothesis:	Initiation of osimertinib decreases the hazard of all-cause mortality as compared to initiation of erlotinib or gefitinib
Exposure contrast:	Initiation of osimertinib vs. initiation of erlotinib or gefitinib
Outcome:	Time to all-cause mortality (overall survival)
Databases used:	EDB1
Analytic software:	R 4.3.2. Version control of code and R packages will be established through git and Posit package manager, respectively. All packages are frozen to their most recent version as of April 24, 2024.
Model(s): (provide details or code)	See example code https://drugepi.gitlab-pages.partners.org/encore/flaura-nct-02296125/ (access only through MGB network for authorized personnel)
Confounding adjustment method	Name method and provide relevant details, e.g. bivariate, multivariable, propensity score matching (specify matching algorithm ratio and caliper), propensity score weighting (specify weight formula, trimming, truncation), propensity score stratification (specify strata definition), other. 1:1 propensity score nearest neighbor matching without replacement and a caliper of 1% of propensity score standard
Ministration of the	deviation
Missing data methods	Name method and provide relevant details, e.g. missing indicators, complete case, last value carried forward, multiple imputation (specify model/variables), other.
	Multiple imputation by chained equations using a random forest imputation model across all covariate types. The number of imputed datasets will be determined by the average proportion of missing values across all partially observed covariates. Imputation models will include all variables of the substantiative model, i.e., exposure, outcome, confounders/prognostic factors and additional auxiliary covariates.
Subgroup Analyses	List all subgroups
	In subgroup analysis, multiple imputation, propensity score matching and balance assessment will be conducted within each subgroup separately. The treatment effect will be estimated in the combined dataset by fitting a Cox proportional-hazards model that will include the exposure, the subgroup covariate of interest, and the treatment-by-subgroup interaction term. 1. Sex (Male, Female)
	2. Age (<65, ≥65)* 3. Resp (athricity (Agian Non Agian)*
	3. Race/ethnicity (Asian, Non-Asian)*4. Smoking history (current/former, never)5. ECOG (0, 1)*

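### The protocol gives EDB1, the only primary-analysis database, two disease scopes, and states no handling for time since metastasis in patients who have none

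*Protocol*

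**What the plan says.** **EDB1 as metastatic only.** Section 6.6.4 introduces the exposure as "initiation of osimertinib versus erlotinib or gefitinib in a 1L metastatic setting". Under EDB1 it then says of the line-of-therapy table: "The LOT implicitly only considers regimens that were given as part of a metastatic disease setting". The setting row of Table 1 likewise names first-line metastatic disease.

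**EDB1 as advanced, including locally advanced.** Section 6.6.2 states: "Since locally advanced line settings are readily curated in EDB1 only, we will restrict the analysis in EDB2 and EDB4" to patients with metastases. No such restriction is placed on EDB1. Table 2 has "Treatment needs to be first-line for advanced (EDB1) or metastatic (EDB2) disease". The population row of Table 1 covers locally advanced as well as metastatic disease and describes the EDB1 lines as advanced/metastatic. Table 3 samples EDB1 on a confirmed diagnosis of advanced NSCLC.

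**The covariate.** Table 5 defines `c_time_met_dx_to_index` as "Time in days between earliest evidence of a metastatic and index date", encoded as continuous. The same table has a TRUE/FALSE flag, `c_met_pre_index`, for any metastasis between initial diagnosis and index date, both ends included.

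**Missing data.** Table 7 specifies "Multiple imputation by chained equations using a random forest imputation model across all covariate types", with all confounders, prognostic factors and auxiliary covariates in the imputation models.

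**EDB4 timing.** In section 6.6.4, "patients are only considered if there is any evidence of a metastatic diagnosis before the index date". Figure 2 has the same order, and Table 1 also requires the evidence to precede initiation. Section 6.6.2 accepts evidence before or on the index date.

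**The concern.** The study is judged on concordance with one particular trial, and section 6.6.2 reports that 5% of that trial's patients were locally advanced. A reader has to know whether the primary cohort keeps that stratum. As written, someone following 6.6.2 and someone following 6.6.4 could describe, or build, different EDB1 cohorts.

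The second matter depends on how the first is settled. For a patient without metastasis, time since first metastasis is not an unrecorded number; it does not exist. A rule that imputes every blank does not distinguish the two cases. The blank could also enter the missingness diagnostics of section 6.7.1 as though it reflected a missing-data mechanism, and could count towards the average missingness that sets the number of imputations.

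**Working it through.** Most of this check is a comparison of text; the short calculation in step 5 sizes only the scope question.

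1. **Is the scope conflict merely loose terminology?** No. Section 6.6.2 separates locally advanced from metastatic disease and sets different eligibility by database on that basis. Section 6.6.4 then uses one identical sentence for EDB1 and EDB2, the two databases that 6.6.2 treats differently. For further detail 6.6.2 refers to a section 6.4.4, which does not exist. The exposure section is 6.6.4, so a reader who follows the evident intention arrives at the statement that contradicts 6.6.2.

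2. **Does the protocol allow for patients without metastasis?** Yes. `c_met_pre_index` has FALSE as a permitted value.

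3. **What happens to the time variable for them?**
   - Table 5 gives no value for this case.
   - Table 7 exempts no covariate or type of blank from imputation.
   - Figure 1 lists time from first evidence of metastatic disease among the baseline covariates, and section 6.6.7 says the most comprehensive model will be fitted in each database.
   - Read together, the general rule would treat the blank as missing. This is an inference from the general rule; no sentence says so for this variable.

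4. **What would the diagnostics make of it?** The blank is tied to an observed flag, so observed covariates would predict it well. Table 6 reads that as missing at random, although the correct label is not applicable.

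5. **Size of the scope question.** The plan's own figure is 80% power at HR 0.8, two-sided alpha 0.05 (section 10.3, Schoenfeld). The event count is not in the text, so the figure can only be solved backwards. With 1:1 allocation, D = 4 × (1.960 + 0.842)² / (ln 0.8)² = 4 × 7.849 / 0.0498 ≈ 631 events. Suppose the metastatic-only reading were enforced and a share s of events dropped out in proportion to patients. Then power = Φ(√(631(1 − s)/4) × 0.2231 − 1.960).
   - s = 2%: 618 events, 79.2%
   - s = 5%: 599 events, 78.0%
   - s = 10%: 568 events, 75.8%
   - s = 20%: 505 events, 70.8%

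   Only the 5% has a source, and it is the trial's share. The EDB1 share is not given and the other values merely show the range. This does not challenge the stated 80%.

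6. **EDB4.** A patient whose metastasis is first recorded on the day of initiation is excluded under section 6.6.4 and included under section 6.6.2. EDB4 enters only sensitivity analysis #11.

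**The case against.** The strongest reply is that this is one sentence copied from EDB1 to EDB2. The population row of Table 1, Table 2 and Table 3 describe EDB1 correctly, so no careful reader is misled. That explanation is plausible, but the setting row of Table 1 repeats the narrower scope, and the conflict concerns the only primary-analysis database. It still needs correcting.

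On the covariate the reply carries more weight. The value returned for non-metastatic patients is set by a derivation function documented in an appendix that is not at hand, and it may already be handled there. Figure 9, which shows the EDB1 propensity covariates, is not shown. Section 6.6.7 says that some listed covariates are auxiliary and that not all are available in every database. Special-value coding can also be left to an analysis plan. These points stand. What remains is narrower: the protocol fixes a general imputation rule with no exception, beside a covariate that needs one if locally advanced patients are included.

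A reader might go further and infer that non-metastatic patients will be matched on invented metastatic histories. The documents do not support that. Matching is on a single propensity score, and Table 5 also lists the metastasis flag, number of metastatic sites, de novo metastatic status and stage, all of which can carry the true status.

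A reader might also see a conflict for EDB2, between a line table that is implicitly metastatic and an explicit requirement for metastases. Those are compatible: Table 1 calls the EDB2 lines advanced/metastatic, and the explicit check is a second filter on top.

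**Conclusion.** The scope contradiction for EDB1 is established from the text and should be resolved. The covariate point holds conditionally: if locally advanced patients are included, time since metastasis is undefined for those without metastasis, no handling is stated, and the general rule would treat the blank as missing. Model membership, the function's default and the number affected cannot be confirmed because Figures 6 and 9 and the code documentation are not available. The effect on the hazard ratio is probably small, assuming an EDB1 share near the trial's 5% and no marked difference between arms.

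Two stronger statements should not be drawn. One is that a known fraction of EDB1 patients would receive a fabricated value; the protocol gives no EDB1 share and does not say what the function returns. The other is that the locally advanced patients have better prognosis and would bias the estimate in a known direction; no figure in the document supports this.

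The EDB4 timing difference is real, but it concerns same-day patients in one sensitivity analysis and cannot change the primary estimate.

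**What to change.** 1. Check the EDB1 line table, then make section 6.6.4 and the setting row of Table 1 agree with the population row of Table 1, Table 2 and section 6.6.2. If locally advanced patients are included, say locally advanced or metastatic for EDB1. Correct the 6.4.4 cross-reference at the same time.

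2. In Table 5, set `c_time_met_dx_to_index` to a fixed value, for example 0, when `c_met_pre_index` is FALSE. Keep the flag in the propensity model whenever the time variable is used, because 0 alone would equate no metastasis with one first recorded on the index date. Leave these cells out of imputation and the missingness diagnostics; a patient flagged TRUE without a date remains genuinely missing. The flag's window opens at initial diagnosis while the time variable's is unbounded, so confirm that no patient flagged FALSE has an earlier metastasis date.

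3. State one timing rule for EDB4 metastatic evidence in Table 1, section 6.6.2, section 6.6.4 and Figure 2. Before or on the index date would match section 6.6.2 and the definition of `c_met_pre_index`.

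The cost is a few lines of wording and one recode in the covariate function. If EDB1 already includes locally advanced patients, no patients are lost from the primary cohort.
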